		
Justification: We are aiming to include participants who can benefit from the treatment to reduce postoperative pain at home and have seen that there is a time lag in pain which potentially increases after discharge. Therefore, we are amending the final inclusion criteria from Postop pain VAS <math>\geq 5</math> in PACU, where analgesia can still be in effect, to VAS <math>>0</math> postop which will better capture the population of interest.
 
2) Revising the subject demographics questionnaire Justification: We have added 'Procedure to be Performed, Physician performing procedure, Tissue to be Operated On and Additional procedure details (such as splints, etc.)' to the demographic form to capture additional information that will allow us to segment results of the primary endpoint of acute change in peak postoperative pain
 
3) Updated Post-op timelines day 7 and day 14 to allow follow-up up to 21 post-surgeries to accommodate change in patient and clinic scheduling that occur for varying reasons
 
4) Updated Study Population to expand scope to include patients electing for functional nasal surgery, common among patients requiring functional rhinoplasty or reconstructive surgery
 
5) Rephrasing Compensation language

V1.1	1.17.2024	
Increased recruitment numbers from 100 to 130. Justification: due to high drop-out rate post randomization; there is the need to increase the recruitment numbers to reach the target of 60 completed participants.

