## STUDY SUMMARY:

Title	Utilization of a microcurrent device for postoperative pain following functional endoscopic sinus surgery: a randomized controlled trial
Purpose	The purpose of this study is to investigate whether daily use of a microcurrent neuromodulation device will decrease the pain experienced by patients in the days following functional nasal and sinus surgery, including pain during postoperative debridement following Endoscopic sinus surgery
Study Design and Duration	A prospective randomized controlled study of 60 recruited subjects undergoing functional nasal or sinus surgery. Enrolled subjects will be randomized (1:1) to receive either an active neuromodulation study device or a sham device that appears identical to the active device while emitting no therapeutic microcurrent. Subjects will self-treat with the device at home and will be followed for a minimum of 2 weeks after surgery up to 21 days post-surgery.
Target Subject Population	60 subjects undergoing functional nasal or sinus surgery
Subject Inclusion Criteria	
 
• Scheduled for FESS or Functional Rhinoplasty
 
• Possessing an American Society of Anesthesiologists physical status classification of I or II
 
• Age <math>\geq 18</math>
 
• Possess the capacity to give informed consent
 
• Able to read write and understand English or Spanish
 
• Able to attend follow up visits at postop Visit 1 (within 0 – day 14) and post-op Visit 2 (within 10 – 21 days)
 
• Postop pain VAS <math>> 0</math> in PACU phase II
 

Subject Exclusion Criteria	
 
• Does not meet inclusion criteria
 
• History of chronic pain
 
• Experiencing chronic pain requiring opioids at baseline and/or who are under the care of pain management specialists
 
• Seizure disorders
 
• Undergoing planned or unplanned additional procedures at the time of surgery
 
• Planned procedure involves nerve cryoablation
 
• In custody of the state
 
• Prisoners
 
• Known to be pregnant
 
• Implanted cranial metallic components or devices including deep brain stimulators or cochlear implants
 
• Has an implanted or external worn cardiac device including pacemakers, automated implantable cardioverter defibrillator (AICD), or any other cardiac electric devices (including non-implanted devices, e.g. defibrillator vest)
 

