**Exclusion Criteria**

- Does not meet inclusion criteria
- History of chronic pain
- Experiencing chronic pain requiring opioids at baseline and/or who are under the care of pain management specialists
- Seizure disorders
- Undergoing planned or unplanned additional procedures at the time of surgery

10 of 20

CONFIDENTIAL – May not be reproduced without written permission from Icahn School of Medicine at Mount Sinai and Tivic Health Systems Inc

- Planned procedure involved nerve cryoablation
- In custody of the state
- Prisoners
- Known to be pregnant
- Implanted cranial metallic components or devices including deep brain stimulators or cochlear implants
- Has an implanted or external worn cardiac device including pacemakers, automated implantable cardioverter defibrillator (AICD), or any other cardiac electric devices (including non-implanted devices, e.g. defibrillator vest)

- **STUDY PROCEDURES**

All study procedures involving subject participation will be conducted according to good clinical practices (GCP) and in compliance with the principles enunciated in the Declaration of Helsinki. All study procedures will be performed at an Investigational Site, under the direction of an Investigator or designee, and at which this protocol will be approved by:

Icahn School of Medicine IRB  
 [name]  
 [name]

- **Subject Screening**

Subjects with a planned functional nasal or sinus surgery will be recruited with the recommendation of the attending physician during their preoperative office visit. The attending physician or research personnel will determine if the subject meets inclusion criteria and does not meet exclusion criteria during their routine preoperative visit (with the exception of postop pain).

- **Randomization**

Eligible subjects that elect to enroll will be randomized via block randomization and assigned to either active or sham study device groups.

- **Blinding**

The study will be double-blind – neither the investigators nor the study subjects will know which group is receiving active or sham treatment. Unblinding will occur after all data has been collected for all study subjects.

- **Study procedure**

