Patients undergoing standard functional nasal or sinus surgery will be recruited with the recommendation of the attending physician during their preoperative office visit. The attending physician or research personnel will determine if the subject meets inclusion criteria and does not meet exclusion criteria during their routine preoperative visit (with the exception of postop pain). If the patient elects to enroll in the study, the following data will be collected from their medical record:

- Basic demographic information: age, sex, insurance status, race and ethnicity
- Medical history: history of opioid use or chronic pain, medication list, allergies, preoperative pain level, other past medical history

In their final preoperative visit, subjects will complete the Sinonasal Outcome Test 22 (SNOT22) and a modified version of the Nasal Obstruction Symptom Evaluation (NOSE). Patients will be instructed by study staff on how to correctly self-administer the device to the periorbital skin. Subjects will be randomized in a 1:1 fashion to one of two groups and given either an active study device or a sham device that appears identical to the active device while emitting no therapeutic microcurrent. These devices will be labeled "A" or "B" depending on the group randomization. Both groups will be instructed to use the device on postoperative days 0-21 and sent home with instructions.

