- How many oxycodone 5 mg have you taken in the last 24 hours?

- Were you able to complete your daily work activities?
- Were you able to complete your daily non-work activities?

Subjects will return to clinic for their first two postoperative visits o . On postoperative V1 and V2 subjects will complete a modified version of the NOSE questionnaire to quantify changes in congestion and nasal obstruction. Post-op V2 subjects will complete the SNOT-22 to capture other sinonasal symptoms. For patients undergoing debridement, upon arriving in clinic, subjects will be instructed to record their current pain level via VAS in their pain diary before and after they self-administer treatment with the study device. They will subsequently record their pain levels during and after the debridement. During the second postop visit, subjects will be asked to complete a user experience questionnaire assessing their satisfaction with the study device and safety/tolerability.

- **Data analysis**

All data will be tabulated. The difference between the symptom scores before and after treatment will be computed for each individual in the study. Differences in change scores will be compared across treatment groups.

An appropriate two-sided statistical test (paired t-test or repeated measure ANOVA) will be used to assess the pre and post differences in symptom severity.

- **STUDY ENDPOINTS**

This study is intended to assess the analgesic efficacy and safety of the study device after functional nasal or sinus surgery. The primary endpoint is the acute change in peak postoperative pain score 10 minutes after treatment.

Auxiliary outcomes include:

- Pain at 1 hour, 2 hours, 4 hours after device treatment
- Pain before, during, and after debridement (applicable to FESS patients)
- Postoperative debridement compliance (applicable to FESS patients)
- Self-report of congestion and nasal obstruction severity
- Total opioid and/or acetaminophen consumption (the former calculated in oral morphine equivalents)
- Patient satisfaction
- Safety and tolerability
- Direct and indirect cost of pain management as calculated by total medications used and number of days missed from usual daily activity
- Utilization of additional healthcare resources (including telephone encounters and visits to any healthcare provider regarding postoperative pain)

- **INDUSTRY COLLABORATOR AND INVESTIGATOR OBLIGATIONS**

- **IRB Review/Approval/Reporting**

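### The trial pools sinus and functional nasal surgery but uses procedure in neither the randomisation nor the arm comparison; adding it as a model factor is a cheap gain in precision, not the repair of a bias.

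*Combined protocol and SAP*

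**What the plan says.** **Population.** The Study Summary admits patients "Scheduled for FESS or Functional Rhinoplasty", while the Inclusion Criteria section uses the broader category of functional nasal or sinus surgery. The title names only endoscopic sinus surgery, and the amendment log records the widening of the population. Patients "Undergoing planned or unplanned additional procedures at the time of surgery" are excluded, so read literally the two procedure groups do not overlap.

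**Randomisation.** The Randomization section says: "Eligible subjects that elect to enroll will be randomized via block randomization and assigned to either active or sham study device groups". The Study procedure section adds that "Subjects will be randomized in a 1:1 fashion to one of two groups", at the final preoperative visit. No block size or stratification factor is given.

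**Use of procedure.** The amendment log explains that procedure, operating physician, tissue and further details were added to the demographics form to "capture additional information that will allow us to segment results of the primary endpoint of acute change in peak postoperative pain". Study Endpoints marks debridement pain and debridement compliance as applying to FESS patients, and the visit schedules do the same for debridement pain recording.

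**Analysis.** Data analysis computes before-after differences and compares them between arms. It names no covariate, subgroup or interaction for procedure. The only sample size target, under Subject Population, is 60 for the mixed population, with 130 to be recruited.

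**The concern.** The study team regards procedure as relevant enough to record it for segmenting the primary result, and the plan already handles the two groups differently for debridement. Procedure is known before allocation, yet neither the randomisation nor the analysis uses it as described.

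Three things are at stake:

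- If outcomes differ by procedure, a chance imbalance in procedure mix moves the arm difference, and the unexplained variation widens every pooled interval.
- Debridement pain is part of the stated purpose, but it can be assessed only in a FESS subset whose size is not given and whose balance between arms is not controlled.
- Segmentation that never reaches Data analysis would be post hoc.

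**Working it through.** **Inputs from the documents:** 60 participants, 1:1 allocation, 130 recruited. The 60 cannot be reproduced, because no effect size, SD, alpha or power is given. The step from 130 to 60 implies a loss of 1 − 60/130 = 53.8%.

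**Assumptions:** a smaller procedure group of 12, 18 or 30 out of 60 (20%, 30%, 50%), because the documents give no share. Block size 4, all 130 randomised, random retention of 60, and procedures mixed throughout recruitment.

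**Step 1: exactly 30 per arm, procedure ignored.** Let X be the number of the smaller group's *m* subjects who fall in one arm. X is hypergeometric (60, *m*, 30), and the gap in procedure share between arms is |2X − *m*|/30. A gap of 20 points or more means |2X − *m*| ≥ 6. For *m* = 30, the SD of X is √(30 × 0.5 × 0.5 × 30/59) = 1.95.

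**Step 2: 130 randomised in permuted blocks, 60 retained** (5,000 simulated trials per setting), without and with stratification by procedure from the first subject.

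| Smaller group | 20% | 30% | 50% |
|---|---|---|---|
| Gap ≥10 points, 30 per arm | 33% | 40% | 44% |
| Gap ≥20 points, 30 per arm | 10% | 16% | 20% |
| Gap ≥10 points, 60 of 130, unstratified | 32.5% | 40.0% | 43.0% |
| Gap ≥20 points, 60 of 130, unstratified | 4.9% | 9.7% | 12.3% |
| Gap ≥10 points, 60 of 130, stratified | 20.8% | 26.2% | 29.0% |
| Gap ≥20 points, 60 of 130, stratified | 1.1% | 2.5% | 3.5% |

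Simulation error and ties at exactly 20 points move the simulated figures by up to about one or two percentage points.

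Much of the exact-30 figure is one boundary outcome. For *m* = 30, the 18 v 12 split alone has probability 2 × C(30,18) × C(30,12)/C(60,30) = 12.6%, which leaves 19.6% − 12.6% = 7.0% for anything larger. If the added procedure entered only in the second half of randomisation, the unstratified chance of a gap of 20 points or more is 3.6%, 6.1% and 5.2% for the three shares.

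**Step 3: effect of a gap.** Shift in the arm difference = gap × difference between procedures. At a 20-point gap and an assumed 1-point procedure difference in VAS change, this is 0.2 × 1 = 0.2 points. With an assumed SD of 2 to 3 points, the standard error is SD × √(2/30) = 0.516 to 0.775. The shift is then 0.2/0.516 = 0.39 down to 0.2/0.775 = 0.26 standard errors.

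**Step 4: precision.** With smaller share *p* and a procedure difference of D within-procedure SDs, leaving procedure out multiplies the variance by 1 + *p*(1 − *p*)D².

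- D = 0.5: 1.04 (*p* = 0.2) to 1.0625 (*p* = 0.5), so 63 to 64 unadjusted subjects do the work of 60 adjusted.
- D = 1: 1.16 to 1.25, so 70 to 75.

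**Step 5: segmented results.** Assuming two-sided alpha 0.05, 80% power and balanced arms, the detectable difference is 0.74 SD overall (30 v 30). Over the three shares it is 0.83, 0.89 and 1.06 SD in the larger group and 1.80, 1.41 and 1.06 SD in the smaller. For an arm-by-procedure interaction it is 1.81, 1.58 and 1.45 SD. Stratification does not repair this.

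**The case against.** The strongest reply is that nothing here is an error. Unstratified block randomisation is unbiased on average, does not raise the type I error, and ordinary standard errors already allow for chance imbalance. That stands in full. A reader might infer that the arm comparison is biased, but the documents do not support this.

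The likely effect is also small. The primary endpoint is a within-person change over 10 minutes, which removes additive differences in pain level between procedures, and nothing in the documents says the acute change differs by procedure. This stands for the primary endpoint. It does not cover the FESS-only outcomes or the segmentation.

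Two other readings are tempting. A reader might infer that splints in rhinoplasty patients distort the nasal obstruction scores. Splints appear only as an example of detail recorded on the form; the documents do not tie them to one operation, say they are in place at Visit 1, or give an effect on NOSE. A reader might also attribute the segmentation plan to the sponsor. The log's sentence is the study team's and says only what the new fields will allow.

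Finally, new lists would come late: the log already reports post-randomisation drop-out, so they would cover only later subjects and the gains in the table would not be reached. Debridement outcomes are already marked as FESS-only, so only the denominator is missing. Both points stand, and they put the model term ahead of the lists. Absence of stratification is itself read from silence; a sentence naming it would settle that part.

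**Conclusion.** The point holds as a worthwhile, low-cost improvement. A pre-randomisation variable that the team already records, and means to use, is missing from both the allocation and the arm comparison as described.

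The cost is chance imbalance and some lost precision. A 20-point gap in procedure mix has probability about 10% to 20% with exactly 30 per arm, or about 5% to 12% with 60 retained of 130, and less if the second procedure entered late. It moves the arm difference by 0.2 times the procedure difference. These figures rest on an assumed 20% to 50% share, random attrition and, for the simulated ones, blocks of four. The size of any procedure difference is unknown, so the shift in points is illustrative.

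**What to change.** Before unblinding, which the Blinding section places after all data are collected, amend Data analysis as follows:

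1. Include planned procedure (FESS versus other functional nasal surgery), as recorded before randomisation, as a factor in the active-versus-sham comparison of the primary endpoint and the NOSE and SNOT-22 outcomes. These two categories also cover the wider wording in the Inclusion Criteria section.
2. Report debridement pain and compliance with the number of FESS subjects per arm as denominator instead of 60.
3. Optional, if recruitment is still open: use separate 1:1 block lists for the two categories for remaining subjects. Attrition erodes the balance this gives, so it supplements step 1 and does not replace it.

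The cost is one model degree of freedom and, for step 3, slightly more list handling. The target of 60 does not change.

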**• SUBJECT POPULATION**

It is anticipated that 130 subjects will be recruited to achieve a sample size of 60 participants, accounting for potential drop-outs and/or screen failures. Any subject that meets all the inclusion and none of the exclusion criteria may be eligible to participate in the study.

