The Investigator will maintain adequate records for the study including the Subject Demographics log, Data Collection sheets, Informed Consent forms, information regarding discontinued subjects, and other pertinent data.

Study participant research data, which is for purposes of statistical analysis and scientific reporting, will be transmitted to and stored on the password protected, encrypted Mount Sinai network, and/or HIPAA compliant REDCap database. Hard copies of study records will be maintained in a locked cabinet within the Department of Otolaryngology, accessible only to the PI and study team members. Participant's

identifiable information will be stored separately and linked to the research data through the use of a unique study identification number. At the end of the study, all study databases will be de-identified and stored for up to 6 years following the completion of the study.

The original study record will consist of:

- Subject Demographics Questionnaire
- Pain Data Sheet(s)
- Debridement Pain Data Sheet
- Medication Data Sheet(s)
- NOSE Data Sheet (Enrollment, Postop V1, Postop V2)
- SNOT22 Data Sheet (Enrollment, Postop V2)
- User Experience Questionnaire

Original study records will be filled out manually by study staff and the study patient, where applicable. If an entry requires change, the correction will be made as follows:

- Draw a single line through the incorrect entry.
- Enter data, date, and initial the change (“white-out”, erasure, or any form of obliteration of data is not permitted under any circumstances).

All fields must be completed in study records. Blank responses will not be interpreted as “none” or “N/A”. If data are not available, a straight line should be drawn through all applicable fields and unused pages, dated and initialed to indicate there was no omission.

After completion of the study, the Investigator will provide the Industry Collaborator with deidentified digital copies of study databases and the original study record.

- **Protocol Deviations/Amendments**

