Investigators may implement a deviation from, or a change of, the protocol to eliminate an immediate hazard(s) to trial subjects without prior IRB approval.

- **Other Reportable New Information and Protocol Deviations/Violations**

17 of 20

CONFIDENTIAL – May not be reproduced without written permission from Icahn School of Medicine at Mount Sinai and Tivic Health Systems Inc

In accordance with local IRB requirements, the following information must be reported within five (5) business days.

- Non-compliance with federal regulations governing human research or with the requirements or determinations of the IRB, or an allegation of such non-compliance
- Failure to follow the protocol due to the action or inaction of the investigator or research staff.
- Breach of confidentiality
- Premature suspension or termination of the research by the sponsor or investigator.

- **Adverse Event Reporting**

A significant adverse event (SAE) is one that has a serious adverse effect on the health or safety of a subject or causes any life-threatening problem or death of the study subject.

All SAEs should be recorded by the Investigator and reported by the Investigator to the Industry Collaborator and to the IRB the next business day after the Investigator becomes aware of the SAE.

The Investigator will collect adverse effects information and will report serious and unanticipated adverse effects to the Industry Collaborator and IRB. The Investigator will terminate the study within five working days if the Investigator and Industry Collaborator determine that the adverse system effects present an unreasonable risk to subjects (21 CFR 812.46(b) (2)).

An adverse event (AE) during a clinical evaluation is “any untoward medical occurrence, unintended disease or injury, or untoward clinical signs (including abnormal laboratory findings) in subjects, users or other persons, whether or not related to the investigational medical device.” It is not dependent on whether the event is considered to be related to the investigational product or the study. An adverse event includes events not seen at the beginning of the study or worsened if present at the beginning.

All AEs observed by the Investigator or reported by the subject will be documented (including all symptoms) and included in the study file.

- **Potential Benefits**

There is no guaranteed benefit to a subject for participation in this study.

- **COST**

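### Safety/tolerability is actively asked about only once, at Visit 2, so subjects who do not reach that visit miss the only solicited assessment, and adverse events before it are captured without a schedule, standard question or listed log

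*Combined protocol and SAP*

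**What the plan says.** The Study Endpoints section gives safety equal billing with analgesia as an aim: "This study is intended to assess the analgesic efficacy and safety of the study device after functional nasal or sinus surgery". The Study Summary likewise shows two endpoints, analgesic efficacy and safety. In the ranking that follows, pain is the sole primary endpoint ("The primary endpoint is the acute change in peak postoperative pain score 10 minutes after treatment"), and safety and tolerability is one of nine auxiliary outcomes. Another auxiliary outcome is "Utilization of additional healthcare resources (including telephone encounters and visits to any healthcare provider regarding postoperative pain)".

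Under Study procedure, the one planned enquiry about safety is: "During the second postop visit, subjects will be asked to complete a user experience questionnaire assessing their satisfaction with the study device and safety/tolerability". The Study Participant Timeline puts that visit at days 12 to 21; the inclusion criteria in the Study Summary allow days 10 to 21.

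Two other sections bear on the point. Data Retention introduces its list of forms with "The original study record will consist of" and names seven, the last being the "User Experience Questionnaire". Adverse Event Reporting places a duty on the investigator to collect adverse effects, and adds: "All AEs observed by the Investigator or reported by the subject will be documented (including all symptoms) and included in the study file".

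On numbers, Subject Population anticipates 130 recruits for a sample of 60, "accounting for potential drop-outs and/or screen failures". The amendment log gives heavy loss after randomization as the reason for raising recruitment to 130.

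**The concern.** Treatment is mostly self-administered at home for up to three weeks, where the investigator sees little. If subjects are asked about side effects only at the last visit, the answers come only from those who attend it. A subject who found the device unpleasant, stopped and did not return would add nothing to the questionnaire data, and no other procedure prompts that subject to report.

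Two things raise the stakes here. The protocol expects substantial loss. It also cites little earlier safety experience with this configuration: a four-person pilot, with a waveform modified from that of the cleared product. This trial could become a main source of tolerability data for the device. If the tendency to drop out after a side effect differs between active and sham, the comparison between arms is affected as well as the overall rate.

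**Working it through.** **Step 1. Where is safety solicited?** Contacts as listed in the timeline, the visit lists and Study procedure:

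| Contact | Adverse-effect question described? |
|---|---|
| Enrollment visit | No (before treatment) |
| Recovery unit, day 0 | No; pain scores only |
| Staff phone call, day after surgery | No; a reminder to use the device |
| Daily diary at home | No; pain, number of device uses, two drug counts, work and non-work activity |
| Visit 1 | No; nasal obstruction score, pain around device use and debridement |
| Visit 2 | Yes; user experience questionnaire |
| Early stop | No contact described |

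There is one solicited assessment, and it falls at the end.

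**Step 2. Which forms hold the data?** The seven listed records are demographics, pain, debridement pain, medication, nasal obstruction score, SNOT-22 and user experience. The questionnaire that carries the safety items is therefore a listed form. An adverse-event log is not listed, and neither is a form for healthcare contacts. Data Retention also says that blanks are not to be read as a negative answer. Without an adverse-event field, a subject with no event cannot be told apart from one who was never asked.

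**Step 3. How many could lack the questionnaire?** The plan gives no drop-out rate, so 130 cannot be re-derived; only the implied loss can be computed. Taking the 60 as subjects who complete Visit 2:

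- 130 − 60 = 70, and 70/130 = 53.8%.

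This is a ceiling for device users. The 70 mixes drop-outs with screen failures. Subjects are randomized and given a device before surgery, while the pain check that completes eligibility and the first treatment both happen afterwards. Some losses after randomization may therefore be people who never used a device. With 1:1 allocation, device users per arm lie between 60/2 = 30 and 130/2 = 65.

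**Step 4. Precision.** With no events among n subjects, the one-sided 95% upper limit for the event rate is 1 − 0.05^(1/n):

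- n = 30: 9.5%
- n = 45: 6.4%
- n = 65: 4.5%

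These figures show what a larger safety denominator gains in precision. They do not measure bias.

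**Step 5. Bias, illustrated under assumed rates.** Let p be the true proportion of users with an adverse effect, and r the chance of reaching Visit 2 with an effect relative to without one. The proportion seen among attenders is p·r / (p·r + 1 − p). The overall completion rate cancels out.

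| p | r | Seen at Visit 2 |
|---|---|---|
| 10% | 1 | 10% |
| 10% | 0.5 | 0.05/0.95 = 5.3% |
| 10% | 0.25 | 0.025/0.925 = 2.7% |
| 5% | 0.5 | 0.025/0.975 = 2.6% |
| 20% | 0.5 | 0.10/0.90 = 11.1% |

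Neither p nor r comes from the documents. If attendance does not depend on side effects (r = 1), there is no bias. If affected subjects are more likely to attend, the error runs the other way.

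**The case against.** The strongest reply is that the protocol does not confine safety data to Visit 2. Adverse Event Reporting obliges the investigator to collect adverse effects and to document all events observed or reported, related to the device or not, in any subject. Data Retention requires information on discontinued subjects to be kept. Most subjects are under the principal monitor's own care, and safety is reviewed every six months. Both clinic visits are routine postoperative appointments, so a subject who stops using the device may still attend them.

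Much of this stands, and it rules out several stronger readings that a reader might infer:

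- **That safety has no form.** The questionnaire that assesses it is listed. What is missing from the list is an adverse-event log.
- **That early stoppers are excluded from safety altogether.** They miss the solicited assessment but remain covered by the general duty.
- **That more than half of device users will be lost.** The 54% includes screen failures and possibly people who were never treated.
- **That an event leading to drop-out is counted as no event.** A missing questionnaire is absent from numerator and denominator alike.
- **That safety is a co-primary endpoint.** The Study Endpoints section ranks it as auxiliary.

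The individual data sheets are also not reproduced, so an item on one of them cannot be excluded.

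The reply does not supply a schedule, a standard question or a contact at early stopping. The general duty says that events are to be collected without saying how. For a treatment used at home, that leaves subjects between visits to volunteer reports, and the six-monthly review can examine only what was collected.

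**Conclusion.** The concern holds in a limited form. Followed as written, the plan obtains solicited safety/tolerability data once, from those who attend Visit 2. Before that visit, and in subjects who stop before it, capture is required in general terms but is unscheduled and has no listed log; healthcare contacts for pain have no listed form either. Apart from a general statement that all data will be tabulated, Data analysis gives no safety population, adverse-event summary or comparison between arms.

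At most 70 of 130 recruits (54%) could lack the questionnaire, if the 60 are those who complete Visit 2; among device users the number may be much lower. Selective observation is therefore a plausible risk, made more so by the heavy post-randomization loss that the amendment log reports. Underestimated harm and a difference between arms are possibilities, not results: the documents give no adverse-event rate and no link between side effects and attendance. The primary endpoint is not affected. The repair is cheap and should be made.

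**What to change.** 1. Add two items to the existing daily diary: one on new symptoms or side effects, and one on calls or visits to any provider about pain.
2. Give the safety/tolerability items of the Visit 2 questionnaire, by phone or at device return, to anyone who stops before Visit 2.
3. Add an adverse-event log to the list of study records under Data Retention.
4. State in Data analysis that safety will be reported by arm for every subject who used a device at least once, and show how many of them answered the solicited items.

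The cost is slightly more diary burden, one log form, and a short call to early stoppers by staff who already phone subjects after surgery. No efficacy procedure changes, and neither does the recruitment figure.
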